| Data Element   | PHARMO (Netherlands)  | National Registers, Denmark                             | National Registers, Sweden                              |
|--|---|---|---|
| Lifestyle risk factors (smoking status, BMI, alcohol intake) | Yes, if recorded by GPs   | Yes, if recorded by GPs                                 | Yes, if recorded by GPs                                 |
| Data availability  | Annual  | Since 1994  | Since 2005  |
| Updates  | Pharmacy data: 2 months
All other data: annual; available following Q3-Q4  | Annual  | Annual  |
| Approximate time lag   | No  | 1 year  | 2012 data will be available in 3Q-4Q 2013               |
| Data transfer  | Review by the independent compliance committee STIZON/ PHARMO Institute
This committee consists of representatives of the individual data suppliers and is chaired by a privacy expert | No, requires collaboration with local investigator      | No, requires collaboration with local investigator      |
| Approval process   | Data application and ethics committee approval required   | Data application and ethics committee approval required | Data application and ethics committee approval required |

ATC = Anatomical Therapeutic Chemical; BMI = Body Mass Index; GP = General Practitioner; ICD-9-CM = *International Classification of Diseases, 9th Revision, Clinical Modification*; ICD-10 = *International Statistical Classification of Diseases and Related Health Problems, 10th Revision*; ICD-10-CM = *International Classification of Diseases, 10th Revision, Clinical Modification*; ICPC = *International Classification of Primary Care*; NCSP = *Nordic Medico-Statistical Committee's Classification of Surgical Procedures*.

1 Eurostat. 2013. Available at: website: [epp.eurostat.ec.europa.eu/tgm/table.do?tab=table&init=1&language=en&pcode=tps00001&plugin=1](http://epp.eurostat.ec.europa.eu/tgm/table.do?tab=table&init=1&language=en&pcode=tps00001&plugin=1). Accessed January 28, 2014.

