The study period will start on the date of olodaterol launch in each country and will end on the latest date the data are available at the time of data extraction. Anticipated study periods for each data source at the time of data extraction and reporting milestones are shown in [Table 1](#).

Proprietary confidential information © 2017 Boehringer Ingelheim International GmbH or one or more of its affiliated companies

Table 1 Estimated study period in each study data source and reporting milestones

Event	PHARMO, the Netherlands	National Registries, Denmark	IMS RWE LPD, France
Olodaterol launch in country	March 2014	January 2014	October 2015
Data extraction for interim report	Q1 2017	Q1 2017	Q1 2017
Anticipated study period included in interim report ¹	March 2014 – Q4 2015	January 2014 – Q4 2015	October 2015 – Q4 2016
Interim report regulatory milestone	Q3 2017	Q3 2017	Q3 2017
Data extraction for final report	Q1 2018	Q1 2018	Q1 2018
Anticipated study period for final report	March 2014 – Q4 2016	January 2014 Q4 2016	October 2015 – Q4 2017
Final report regulatory milestone	Q3 2018	Q3 2018	Q3 2018

IMS = IMS Health Information Solutions; PHARMO = PHARMO Database Network; Q_n = the quarter of the calendar year; RWE LPD = Real-World Evidence Longitudinal Patient Database.

1. Study periods of observation are estimated based on the following lag times in each data source: PHARMO, approximately 6 to 18 months, Danish registries, approximately 6 to 12 months; IMS RWE LPD, 2 to 7 months.

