4. CHANGES IN THE PLANNED ANALYSIS OF THE STUDY

[figure not shown]
This section includes changes and clarifications in the planned analysis presented in the study protocol.

Number	Date	Section of SEAP	Update	Reason
1	16 Jan 2017	5.1	The time window used in the definition of COPD, asthma, and other respiratory diagnosis has been extended to include 30 days after index date	To take into account differences in recording practices and potential delay in data recording in each data source, e.g., the general practitioner may have recorded the COPD diagnosis a few days after hospital discharge
2	16 Jan 2017	5.1	Patients classified under potential off-label use (with no asthma and no COPD diagnosis) will be further characterised	To describe how many have “probable COPD” based on the use of medications and age, and how many have respiratory conditions other than COPD and asthma
3	16 Jan 2017	5.3	The definition of COPD severity has been modified	To update the algorithm and make it similar to current GOLD 2016 guidelines [P16-00121]
4	16 Jan 2017	5.3	COPD severity will be described among the patients with COPD aged 40 years or older and among patients with COPD aged 39 years or younger	Patients aged 40 years or older are the population most likely to have COPD; description by age groups will facilitate comparisons with published literature where patients with COPD are frequently selected if they are aged 40 or older

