5. OUTCOMES

For each patient, the observation period will start at the index date and look retrospectively for all available historical data and prospectively for up to 30 days after the index date to identify potential off-label use (Figure 1). The index date is defined as the date of the first recorded dispensing/prescription of olodaterol or indacaterol during the study period in each data source (see Table 1). In each country, new users of olodaterol and indacaterol will be identified in the databases, which record information on the medications prescribed by the physicians or dispensed by pharmacies. Evaluation of off-label use and diagnosis of COPD, asthma, or other respiratory conditions will be assessed using all available information in the database before the index date (as far back in time as records in the data source are available)—i.e., 01 Jan 1994 in Denmark, 1998 in PHARMO (1998 for total patient set and 2006 for subset with GP data available), and 1994 in IMS RWE LPD (1994 for GP panel and 2007 for pulmonologist panel) and up to 30 days after index date. Characterisation of new users based on demographic and other non-respiratory comorbidities will be assessed using all available information in the database before the index date, unless otherwise specified. Medication use, severity of COPD, and health care resource utilisation will be assessed for the 1-year period before the index date. Database-specific specifications to define the variables of interest in each data source are included in Section 9.2.

Figure 1 Time periods for defining key study variables

^a“Other respiratory conditions” are respiratory comorbidities other than COPD or asthma recorded at any time before or up to 30 days after index date and will be ascertained using the diseases and codes listed in Table 8. These will be described for the purpose of characterising the study population overall and the patients classified as potential off-label users.

Proprietary confidential information © 2017 Boehringer Ingelheim International GmbH or one or more of its affiliated companies

The type of data available varies in each database and is summarised in [Table 2](#).

Table 2 Selected characteristics of the study databases

Type of data	PHARMO, the Netherlands	National Registers, Denmark	IMS RWE LPD, France
Hospital inpatient discharge diagnoses	Yes	Yes	No
Hospital inpatient procedures	Yes	Yes	No
Hospital/clinic outpatient diagnoses	No	Yes	No

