A diagnosis of COPD or asthma will be defined as having one or more COPD or asthma diagnoses recorded in the database before the index date and up to 30 days following the index date. The *International Statistical Classification of Diseases and Related Health Problems, 10th Revision* (ICD-10) and *International Classification of Primary Care* (ICPC) codes to identify patients with COPD and asthma are detailed in [Table 5](#).

Table 5 ICD-10 and ICPC diagnosis codes to identify patients with COPD and asthma

ICD-10 code description	ICD-10 code ¹	ICPC code ¹
COPD	J41-J44	R95
Chronic bronchitis ²	J41-J42	R78, R91
Emphysema	J43	—
Other COPD	J44	—
Asthma	J45, J46	R96

ICD-10 = *International Statistical Classification of Diseases and Related Health Problems, 10th Revision*;
ICPC = *International Classification of Primary Care*.

1. Data sources use different coding systems with different degrees of granularity; thus, subclassifications will be adapted to each database.
2. The use of ICD-10 code J40 “Bronchitis, not specified as acute or chronic” to define COPD will be assessed in the data source-specific definitions.

Proprietary confidential information © 2017 Boehringer Ingelheim International GmbH or one or more of its affiliated companies

The indication for the prescribing of medications is not recorded in either the PHARMO databases or the Danish National Registries; indication is available but may be incomplete in the IMS RWE LPD. Therefore, when indication is not available, the indication of treatment and potential off-label use of olodaterol and indacaterol will be inferred from COPD and asthma diagnosis recorded at any time before or on the index date or up to 30 days after the index date and from the clinical review of information in computerised patient profiles. In addition, the time since first COPD diagnosis, i.e., time between the first recorded diagnosis of COPD in the database and the index date, will be ascertained for new users of olodaterol and indacaterol. Additional database-specific specifications on COPD, asthma, and on-label/off-label use are presented in Section [9.2](#).

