6.3 PATIENT SETS ANALYSED

Patients in the study will be required to meet the following criteria, as ascertained from each of the data sources:

- Receive a first dispensing for single-agent formulations of olodaterol or indacaterol during the study period with no prescriptions/dispensings ever before (see study period in [Table 1](#))
- Have at least 1 year of continuous enrolment in the data source immediately preceding the index date
- Have available data and no implausible values for age (< 0 years and > 120 years) or sex

Two study medication groups will be created: (1) a group of new users of olodaterol and (2) a group of new users of indacaterol. Inclusion in the study cohort as a new user in one of the two groups does not preclude the patient from being included as a new user in the other group if the inclusion criteria are met. The number of patients included in both groups will be reported.

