7. PLANNED ANALYSIS

The different research centres will use the core final study protocol and SEAP to conduct analyses in the respective data sources and generate output that will be provided to the coordinating centre (RTI Health Solutions), which will generate the study reports.

All the analyses will be conducted separately for olodaterol and indacaterol new users and further stratified by LABA-naïve patients and switchers. Analysis for each report (i.e., interim and final) will include data on all patients starting treatment with olodaterol or indacaterol from the start of such treatment during the study period up to the latest available data (see anticipated study periods for interim and final reports in [Table 1](#)). The interim analysis will include all the analyses described in the present section.

Tables and figure shells describing all planned analyses have been developed (see separate Word file) and will be adapted to each data source. For each data source, an attrition table will be generated to describe the impact on the study size at each step of applying the study inclusion and exclusion criteria (Figure Shell 1).

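### New users are accepted up to the last available data date, yet on-label status needs codes to day 30 after index: a small downward bias in the on-label share

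*SAP*

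**What the plan says.** **Entry.** SAP Section 3 states that the study period "will end on the latest date the data are available at the time of data extraction". Section 5 defines the index date as the "date of the first recorded dispensing/prescription of olodaterol or indacaterol during the study period". Section 7 has each report include all patients "from the start of such treatment during the study period up to the latest available data".

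**Classification.** Section 5 looks back over all history and "prospectively for up to 30 days after the index date to identify potential off-label use". Section 5.1 defines COPD or asthma as one or more diagnoses "recorded in the database before the index date and up to 30 days following the index date". Section 4 shows that this window was added on 16 January 2017: it "has been extended to include 30 days after index date", because recording may be delayed. The change table lists no matching change to the entry rule.

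**Eligibility.** Section 6.3 asks patients to "Have at least 1 year of continuous enrolment in the data source immediately preceding the index date". It asks for nothing after index.

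**Unseen codes.** Sections 5.3 and 6.5 treat a condition with no record as absent, and Section 6.5 accepts that this produces misclassification, not missing values.

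Section 6.6 still describes off-label use as assessed from baseline information, with baseline ending at the index date. That does not fit the 30-day window.

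**The concern.** A user who starts treatment within 30 days of the end of the data cannot have a complete window. If that user's first COPD code would have been recorded after the data close, the stated rules take the user as having no COPD and raise no flag. The window was introduced to catch late recording, and it fails for the latest entrants.

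The main outcome is the prevalence of off-label prescribing, so the error falls directly on it. Truncation can only remove COPD codes, so an affected adult can only leave the on-label category. Under the protocol's objective, where off-label means no COPD, the error goes one way. In SAP Table 4 the user lands in off-label if an asthma code is visible, and in potential off-label otherwise. Children, and adults with a COPD code on or before index, are unaffected.

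**Working it through.** **Yardstick.** The plan gives no figure for this effect. Its only precision figures are in protocol Table 9. Exact Clopper-Pearson intervals (the method in SAP 7.5.1) reproduce all 20 entries to one decimal. At 10% prevalence they are 8.0-12.3 for n = 800, a half-width of (12.3 - 8.0)/2 = 2.15 points, and 9.2-10.9 for n = 5,000, a half-width of 0.85.

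**Step 1: share of entrants with an incomplete window.** Study periods come from SAP Table 1, which gives months and quarters only. I assume they run from the first day of the launch month to the last day of the quarter. T is the length in days. With uniform entry the share is 30/T. With linearly rising uptake (an assumption) it is 1 - (1 - 30/T)².

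| Source and report | T | Uniform | Rising |
|---|---|---|---|
| PHARMO final | 1,037 | 2.9% | 5.7% |
| Denmark final | 1,096 | 2.7% | 5.4% |
| France final | 823 | 3.6% | 7.2% |
| PHARMO interim | 671 | 4.5% | 8.7% |
| Denmark interim | 730 | 4.1% | 8.1% |
| France interim | 458 | 6.6% | 12.7% |

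**Step 2: part of the window lost.** Entrants in the last 30 days have 0 to 29 post-index days visible. If late codes are spread evenly over days 1-30, the mean part lost is L = (30 + 29 + ... + 1)/(30 × 30) = 465/900 = 0.517.

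**Step 3: fall in the on-label share.** Let g be the share of new users whose first COPD code falls on days 1-30. The documents do not give it; I use 1% to 20%. The fall is (share from step 1) × 0.517 × g. In percentage points:

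| Source and report | Entry | g = 1% | g = 10% | g = 20% |
|---|---|---|---|---|
| PHARMO final | uniform | 0.015 | 0.15 | 0.30 |
| PHARMO final | rising | 0.03 | 0.29 | 0.59 |
| Denmark final | uniform | 0.014 | 0.14 | 0.28 |
| Denmark final | rising | 0.03 | 0.28 | 0.56 |
| France final | uniform | 0.019 | 0.19 | 0.38 |
| France final | rising | 0.04 | 0.37 | 0.74 |
| France interim | uniform | 0.03 | 0.34 | 0.68 |
| France interim | rising | 0.07 | 0.65 | 1.31 |

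For example, France final, rising, g = 20%: 0.0716 × 0.517 × 0.20 = 0.0074.

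**Step 4: direction within SAP Table 4.** A lost COPD code moves an adult from on-label to off-label (asthma code seen) or to potential off-label (none seen). A lost asthma code in an adult without COPD moves that adult from off-label to potential off-label. The first raises the two non-on-label categories together. The second lowers off-label alone.

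**The case against.** **A rule may exist elsewhere.** SAP Sections 5, 5.1 and 5.3.3 refer to database-specific specifications in Section 9.2, which is not in the text available. A local run-out rule there cannot be excluded. This stands, and the finding is limited to what can be read.

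**PHARMO files.** A reader might infer that PHARMO dispensings run ahead of its GP and hospital records, because protocol Table 8 lists pharmacy data at 2 months and "All other data: annual; available following Q3-Q4". The documents do not support this as a finding. The later SAP Table 1 uses one PHARMO lag of 6 to 18 months. It ends the periods at Q4 2015 for extraction in Q1 2017 and at Q4 2016 for extraction in Q1 2018, which suggests closure on the slower files. The SAP does not say so, but the 30-day tail does not depend on it. If diagnosis records in fact continue past the last accepted index date, the loss shrinks.

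**France.** The largest shares are in the French interim. Yet Section 5.1 infers indication from diagnoses there only when none is recorded, so some users are protected. How many is not stated.

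**Shares are not bias.** Most users in step 1 keep their correct class. The example in SAP 4 is a delay of days, not weeks. If such short delays are typical, L falls well below 0.517 and step 3 overstates the effect.

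**Existing safeguards.** The profile review in Section 5.1 checks whether the window suits each source, and probable COPD is explored among potential off-label users. Neither recovers codes recorded after the extract closes. Interim entrants are included again in the final report, where their windows can be completed. The end of the final period has no such remedy.

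**Conclusion.** The point holds as a minor design gap. On the rules as written in the available text, some adults entering in the last 30 days leave on-label only because their window is cut short. The on-label share is biased down, by about 0.01-0.74 points in the final report and up to 1.3 points in the French interim. Most of these values are well inside the Table 9 half-width for n = 800, but the bias does not shrink as numbers grow. The size rests on the assumed calendar limits, uptake shape, even spread of late codes and g of 1-20%.

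Two stronger readings do not follow:

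- A reader might infer that the off-label percentage itself is inflated. Because asthma codes are lost too, only the sum of off-label and potential off-label has a known sign.
- A reader might infer that olodaterol is affected more, as the newer drug. The documents give no uptake curve, and the protocol says that counts of olodaterol users were not yet available. Rising uptake is a scenario here, not a fact.

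**What to change.** In SAP Sections 3 and 6.3, set the last eligible index date in each source to 30 days before the end of the diagnosis data used for classification. Where linked files close on different dates, use the earliest. Bring the sentence in Section 7 and the periods in Table 1 into line, and reconcile Section 6.6 with the 30-day window. If Section 9.2 already contains such a rule, a cross-reference is enough.

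Under uniform entry this drops 2.7% to 3.6% of final-report entrants (5.4% to 7.2% with rising uptake) and 6.6% in the French interim. If linked files close at different times, the loss is larger by that gap. Precision hardly changes: dropping 6.6% from n = 800 leaves 747, and the interval at 10% prevalence moves from 8.0-12.3 to 8.0-12.4.

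Reporting, by source, how many users have their first COPD code on days 1-30 would replace the assumed g with a measured one.

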4. CHANGES IN THE PLANNED ANALYSIS OF THE STUDY

[figure not shown]
This section includes changes and clarifications in the planned analysis presented in the study protocol.

Number	Date	Section of SEAP	Update	Reason
1	16 Jan 2017	5.1	The time window used in the definition of COPD, asthma, and other respiratory diagnosis has been extended to include 30 days after index date	To take into account differences in recording practices and potential delay in data recording in each data source, e.g., the general practitioner may have recorded the COPD diagnosis a few days after hospital discharge
2	16 Jan 2017	5.1	Patients classified under potential off-label use (with no asthma and no COPD diagnosis) will be further characterised	To describe how many have “probable COPD” based on the use of medications and age, and how many have respiratory conditions other than COPD and asthma
3	16 Jan 2017	5.3	The definition of COPD severity has been modified	To update the algorithm and make it similar to current GOLD 2016 guidelines [P16-00121]
4	16 Jan 2017	5.3	COPD severity will be described among the patients with COPD aged 40 years or older and among patients with COPD aged 39 years or younger	Patients aged 40 years or older are the population most likely to have COPD; description by age groups will facilitate comparisons with published literature where patients with COPD are frequently selected if they are aged 40 or older

5. OUTCOMES

For each patient, the observation period will start at the index date and look retrospectively for all available historical data and prospectively for up to 30 days after the index date to identify potential off-label use (Figure 1). The index date is defined as the date of the first recorded dispensing/prescription of olodaterol or indacaterol during the study period in each data source (see Table 1). In each country, new users of olodaterol and indacaterol will be identified in the databases, which record information on the medications prescribed by the physicians or dispensed by pharmacies. Evaluation of off-label use and diagnosis of COPD, asthma, or other respiratory conditions will be assessed using all available information in the database before the index date (as far back in time as records in the data source are available)—i.e., 01 Jan 1994 in Denmark, 1998 in PHARMO (1998 for total patient set and 2006 for subset with GP data available), and 1994 in IMS RWE LPD (1994 for GP panel and 2007 for pulmonologist panel) and up to 30 days after index date. Characterisation of new users based on demographic and other non-respiratory comorbidities will be assessed using all available information in the database before the index date, unless otherwise specified. Medication use, severity of COPD, and health care resource utilisation will be assessed for the 1-year period before the index date. Database-specific specifications to define the variables of interest in each data source are included in Section 9.2.

Figure 1 Time periods for defining key study variables

^a“Other respiratory conditions” are respiratory comorbidities other than COPD or asthma recorded at any time before or up to 30 days after index date and will be ascertained using the diseases and codes listed in Table 8. These will be described for the purpose of characterising the study population overall and the patients classified as potential off-label users.

Proprietary confidential information © 2017 Boehringer Ingelheim International GmbH or one or more of its affiliated companies

The type of data available varies in each database and is summarised in [Table 2](#).

Table 2 Selected characteristics of the study databases

Type of data	PHARMO, the Netherlands	National Registers, Denmark	IMS RWE LPD, France
Hospital inpatient discharge diagnoses	Yes	Yes	No
Hospital inpatient procedures	Yes	Yes	No
Hospital/clinic outpatient diagnoses	No	Yes	No
General practitioner outpatient diagnoses	Yes, in data subset PHARMO-GP ¹	No	Yes (a panel of 1,200 general practitioners) ²
Specialist diagnoses	Yes, those in the hospital (no outpatient hospital or non-hospital clinics) or as communicated to and recorded by the GP in PHARMO-GP (primary care)	Yes, those in the hospital (inpatient diagnosis) and hospital outpatient clinics (outpatient diagnosis) (not outside the hospital)	Yes (a panel of 40 pulmonologists) ³
Pharmacy-dispensed medications	Yes	Yes	No
Prescribed medications	Yes, in data subset PHARMO-GP ¹	No	Yes

GP = General Practitioner; IMS = IMS Health Information Solutions; PHARMO = PHARMO Database Network; RWE LPD = Real-World Evidence Longitudinal Patient Database.

- 1 For this study, data from the Out-patient Pharmacy Database and the Hospitalisation Database are available for the overall source population (approximately 4 million patients covered); the subcohort PHARMO-GP includes approximately 1 million patients with data in the Out-patient Pharmacy Database, the Hospitalisation Database, and the General Practitioner (GP) Database. The Out-patient Pharmacy Database will be used to identify medication use.
- 2 The GP panel covers a population of approximately 1.8 million active patients.
- 3 The pulmonologist panel covers a population of approximately 55,000 active patients.

The coding of diagnoses, procedures, and medications varies across databases ([Table 3](#)).

Proprietary confidential information © 2017 Boehringer Ingelheim International GmbH or one or more of its affiliated companies

Table 3 Types of diagnosis, procedures, and medication codes in the study databases

Type of code	PHARMO, The Netherlands	National Registers, Denmark	IMS RWE LPD, France
Diagnoses	Hospital: ICD-10 ¹ Primary health care: ICPC ²	ICD-10	Local in-house thesaurus that can be mapped to ICD-10
Procedures	CBV	NCSP version 1.16, 2012	Local in-house thesaurus that can be mapped to ICD-10
Medications	ATC	ATC	/ EphMRA mapped to ATC

ATC = Anatomical Therapeutic Chemical; CBV = Centraal Beheer Verrichtingenbestand (codes), Dutch Hospital Data Foundation–owned registration system for procedures, which links to the Dutch Healthcare Authority (NZa) declaration codes and the Dutch Classification of Procedures; EphMRA = European Pharmaceutical Market Research Association; ICD-9 = *International Classification of Diseases, 9th Revision*; ICD-10 = *International Statistical Classification of Diseases and Related Health Problems, 10th Revision*; ICPC = International Classification of Primary Care; IMS = IMS Health Information Solutions; NCSP = *Nordic Medico-Statistical Committee's Classification of Surgical Procedures*; PHARMO = PHARMO Database Network; RWE LPD = Real-World Evidence Longitudinal Patient Database.

- 1 Hospital codes in PHARMO before 2011 were ICD-9 and CBV. PHARMO will work with ICD-9 codes and map them to ICD-10 codes before conducting the analysis.
- 2 Available for PHARMO-GP, a data subset of PHARMO with information from GPs.

